5.2 Administration of Nivolumab

Nivolumab will be administered at a fixed dose of 240 mg over 30 minutes IV every 2 weeks during radiotherapy, and at 480 mg over 60 minutes IV every 4 weeks for 6 doses after radiotherapy. The first dose will be given prior to the first fraction of radiation (Day 1) on Day -5 (+/- 2 days) and continued every 2 weeks (+/- 2 days). Nivolumab will thus be given in weeks 2 and 4 of radiotherapy.

Adjuvant nivolumab will then be given for a total of 6 additional doses after the completion of radiotherapy every 4 weeks (+/- 7 days), starting in the second or third week after the completion of radiotherapy.

There are no recommended premedications for nivolumab.

Doses of nivolumab may be interrupted, delayed, or discontinued depending on how well the subject tolerates the treatment.

Dose delay criteria apply for all drug-related AEs. Treatment delay up to 6 weeks for nivolumab from the last dose are allowable (any dose delays greater than these will require approval from the medical co-chair).

Radiation therapy should not be delayed.

Dosing modifications:

There will be no dose modifications allowed for the management of toxicities of individual subjects.

Tumor assessments for all subjects should continue as per protocol even if dosing is delayed.

Nivolumab should be delayed for the following:

- Any Grade ≥ 2 non-skin, drug-related adverse event, except for fatigue and laboratory abnormalities
- Any Grade ≥ 3 skin drug-related AE
- Any Grade ≥ 3 drug-related laboratory abnormality with the following exceptions for lymphopenia, aspartate aminotransferase (AST), alanine aminotransferase (ALT), or total bilirubin or asymptomatic amylase or lipase:
 - Grade 3 lymphopenia does not require a dose delay
 - If a subject has a baseline AST, ALT, or total bilirubin that is within normal limits, delay dosing for drug-related Grade 2 toxicity
 - If a subject has baseline AST, ALT, or total bilirubin within the Grade 1 toxicity range, delay dosing for drug-related Grade ≥ 3 toxicity
 - Any Grade ≥ 3 drug-related amylase or lipase abnormality that is not associated with symptoms or clinical manifestations of pancreatitis does not require dose delay. The Medical Co-chair should be consulted for such Grade ≥ 3 amylase or lipase abnormalities.
- Any AE, laboratory abnormality or inter-current illness which, in the judgment of the investigator, warrants delaying the dose of study medication.

Nivolumab Dose Discontinuation Due to Drug-Related AE(s)

Treatment with nivolumab should be permanently discontinued for any of the following:

- Any Grade 2 drug-related uveitis or eye pain or blurred vision that does not respond to topical therapy and does not improve to Grade 1 severity within the re-treatment period OR requires systemic treatment
- Any Grade 3 drug-related bronchospasm, hypersensitivity reaction, or infusion reaction, regardless of duration;
- Any Grade 3 non-skin, drug-related adverse event lasting > 7 days, with the following exceptions for uveitis, pneumonitis, bronchospasm, diarrhea, colitis, neurologic toxicity, hypersensitivity reactions, infusion reactions, endocrinopathies, and laboratory abnormalities:
- Any Grade 3 drug-related uveitis, pneumonitis, bronchospasm, diarrhea, colitis, neurologic toxicity, hypersensitivity reaction, or infusion reaction of any duration requires discontinuation.

- Any Grade 3 drug-related endocrinopathies adequately controlled with only physiologic hormone replacement do not require discontinuation.
- Any Grade 3 drug-related laboratory abnormalities do not require treatment discontinuation except:
 - Grade 3 drug-related thrombocytopenia > 7 days or associated with bleeding requires discontinuation.
 - Any drug-related liver function test (LFT) abnormality that meets the following criteria require discontinuation
 - AST or ALT > 5 -10x ULN for > 2 weeks
 - AST or ALT > 10x ULN
 - Total bilirubin > 5 x ULN
 - Concurrent AST or ALT > 3 x ULN and total bilirubin > 2 x ULN
- Any Grade 4 drug-related adverse event or laboratory abnormality, except for the following events, which do not require discontinuation:
 - Grade 4 neutropenia \leq 7 days
 - Grade 4 lymphopenia or leukopenia
 - Isolated Grade 4 amylase or lipase abnormalities that are not associated with symptoms or clinical manifestations of pancreatitis and decrease to < Grade 4 within 1 week of onset. The Medical Co-chair should be consulted for Grade 4 amylase or lipase abnormalities
 - Isolated Grade 4 electrolyte imbalances/abnormalities that are not associated with clinical sequelae and are corrected with supplementation/appropriate management within 72 hours of their onset
- AST or ALT more than 5 times the upper limit of normal (ULN) or total bilirubin more than 3 times the ULN, for any duration of time
- Grade 3 adrenal insufficiency regardless of whether adequately controlled with physiologic hormone replacement
- Grade 3 myocarditis
- Requirement for 10 mg per day or greater of prednisone or equivalent for management of immune-related adverse reactions for more than 12 weeks
- Any adverse event, laboratory abnormality, or intercurrent illness which, in the judgment of the Investigator, presents a substantial clinical risk to the subject with continued nivolumab dosing.

Criteria to Resume Nivolumab Dosing

Subjects may resume treatment with nivolumab when the drug-related AE(s) resolve(s) to Grade \leq 1 or baseline, with the following exceptions:

- Subjects may resume treatment in the presence of Grade 2 fatigue.
- Subjects who have not experienced a Grade 3 drug-related skin AE may resume treatment in the presence of Grade 2 skin toxicity.
- Subjects with combined Grade 2 AST/ALT and total bilirubin values meeting discontinuation parameters should have treatment permanently discontinued.
- Drug-related pulmonary toxicity, diarrhea, or colitis must have resolved to baseline before treatment is resumed. Subjects with persistent Grade 1 pneumonitis after completion of a steroid taper over at least 1 month may be eligible for retreatment if discussed with and approved by the Medical Co-chair.
- Subjects who received systemic corticosteroids for management of any drug-related toxicity must be off corticosteroids or have tapered down to an equivalent dose of prednisone \leq 10 mg/day.
- Drug-related endocrinopathies adequately controlled with only physiologic hormone replacement may resume treatment.
- Dose delay of nivolumab which results in treatment interruption of > 6 weeks requires treatment discontinuation, with exceptions as noted above.

Nivolumab Infusion Reactions

Since nivolumab contains only human immunoglobulin protein sequences, is unlikely to be immunogenic and induce infusion or hypersensitivity reactions. However, if such a reaction were to occur, it might manifest with fever, chills, rigors, headache, rash, pruritus, arthralgias, hypo- or hypertension, bronchospasm, or other symptoms. All Grade 3 or 4 infusion reactions should be reported within 24 hours as an SAE if criteria are met. Infusion reactions should be graded according to National Cancer Institute (NCI) Common Terminology Criteria for Adverse Event (CTCAE, Version 4.0) guidelines.

Treatment recommendations are provided below and may be modified based on local treatment standards and guidelines, as appropriate:

Treatment Recommendations for Nivolumab Infusion Reactions	
For Grade 1 symptoms: (mild reaction; infusion interruption not indicated; intervention not indicated)	
• Remain at bedside and monitor subject until recovery from symptoms. The following prophylactic premedications are recommended for future infusions: diphenhydramine 50 mg (or equivalent) and/or acetaminophen 325 to 1000 mg at least 30 minutes before additional nivolumab administrations.
For Grade 2 symptoms: (moderate reaction requires therapy or infusion interruption but responds promptly to symptomatic treatment [eg, antihistamines, non-steroidal anti-inflammatory drugs, narcotics, corticosteroids, bronchodilators, IV fluids]; prophylactic medications indicated for ≤ 24 hours)	
• Stop the nivolumab infusion, begin an IV infusion of normal saline, and treat the subject with diphenhydramine 50 mg IV (or equivalent) and/or acetaminophen 325 to 1000 mg; remain at bedside and monitor subject until resolution of symptoms. Corticosteroid and/or bronchodilator therapy may also be administered as appropriate. If the infusion is interrupted, then restart the infusion at 50% of the original infusion rate when symptoms resolve; if no further complications ensue after 30 minutes, the rate may be increased to 100% of the original infusion rate. Monitor subject closely. If symptoms recur, then no further nivolumab will be administered at that visit. Administer diphenhydramine 50 mg IV and remain at bedside and monitor the subject until resolution of symptoms. The amount of study drug infused must be recorded on the electronic case report form (eCRF).• For future infusions, the following prophylactic premedications are recommended: diphenhydramine 50 mg (or equivalent) and/or acetaminophen 325-1000 mg should be administered >30 minutes before nivolumab infusion. If necessary, corticosteroids (up to 25 mg of SoluCortef or equivalent) may be used.
For Grade 3 or 4 symptoms: (severe reaction, Grade 3: prolonged [i.e., not rapidly responsive to symptomatic medication and/or brief interruption of infusion]; recurrence of symptoms following initial improvement; hospitalization indicated for other clinical sequelae [e.g., renal impairment, pulmonary infiltrates]. Grade 4: Life threatening; pressor or ventilatory support indicated).	
• Immediately discontinue infusion of nivolumab. Begin an IV infusion of normal saline and treat the subject as follows: Recommend bronchodilators, epinephrine 0.2 to 1 mg of a 1:1000 solution for subcutaneous administration or 0.1 to 0.25 mg of a 1:10,000 solution injected slowly for IV administration, and/or diphenhydramine 50 mg IV with methylprednisolone 100 mg IV (or equivalent), as needed. Subject should be monitored until the investigator is comfortable that the symptoms will not recur. Nivolumab will be permanently discontinued. Investigators should follow their institutional guidelines for the treatment of anaphylaxis. Remain at bedside and monitor subject until recovery of the symptoms.

In case of late-occurring hypersensitivity symptoms (e.g., appearance of a localized or generalized pruritus within 1 week after treatment), symptomatic treatment may be given (e.g., oral antihistamine or corticosteroids).

Duration of Nivolumab

Nivolumab will be given for a total of 9 doses, as detailed above, or until progressive disease, unacceptable toxicity, withdrawal of consent, or the study ends, whichever occurs first. For all subjects, global deterioration of health status requiring discontinuation of treatment without objective evidence of disease progression at that time is allowed, if necessary.

5.3 Adverse Event Reporting Requirements and Procedure

Purpose

Adverse event (AE) data collection and reporting, which are required as part of every clinical trial, are done to ensure the safety of the patients enrolled, as well as those who will enroll in future studies using similar agents.

- **Routine reporting:** Adverse events are reported in a routine manner at scheduled times during the trial using UPMC coordinating center (for external sites).
- **Expedited reporting:** In addition to routine reporting, certain adverse events must be reported in an expedited manner for timelier monitoring of patient safety and care. The following sections provide information and instructions regarding expedited adverse event reporting.

Definitions

- **Adverse Event (AE):** Any untoward medical occurrence associated with the use of a drug in humans, whether considered drug related. Therefore, an AE can be ANY unfavorable and unintended sign (including an abnormal laboratory finding), symptom, or disease temporally associated with the use of a medicinal product, whether considered related to the medicinal product.
- **Life-threatening adverse event or life-threatening suspected adverse reaction:** An adverse event or suspected adverse reaction is considered "life-threatening" if, in the view of either the investigator or sponsor, its occurrence places the patient or subject at immediate risk of death. It does not include an adverse event or suspected adverse reaction that, had it occurred in a more severe form, might have caused death.
- **Serious adverse event or serious suspected adverse reaction:** An adverse event or suspected adverse reaction is considered "serious" if, in the view of either the investigator or sponsor, it results in any of the following outcomes: death, a life-threatening adverse event, inpatient hospitalization or prolongation of existing hospitalization, a persistent or significant incapacity or substantial disruption of the ability to conduct normal life functions, or a congenital anomaly/birth defect. Important medical events that may not result in death, be life-threatening, or require hospitalization may be considered serious when, based upon appropriate medical judgment, they may jeopardize the patient or subject and may require medical or surgical intervention to prevent one of the outcomes listed in this definition. Examples of such medical events include allergic bronchospasm requiring intensive treatment in an emergency room or at home, blood dyscrasias or convulsions that do not result in inpatient hospitalization, or the development of drug dependency or drug abuse.
- **Suspected adverse reaction:** Any adverse event for which there is a reasonable possibility that the drug caused the adverse event. For the purposes of IND safety reporting, "reasonable possibility" means there is evidence to suggest a causal relationship between the drug and the adverse event. Suspected adverse reaction implies less certainty about causality than adverse reaction, which means any adverse event caused by a drug.

Adverse reaction means any adverse event caused by a drug. Adverse reactions are a subset of all suspected adverse reactions where there is reason to conclude that the drug caused the event.

- **Unexpected adverse event or unexpected suspected adverse reaction:** An adverse event or suspected adverse reaction is considered "unexpected" if it is not listed in the investigator brochure or is not listed at the specificity or severity that has been observed; or, if an investigator brochure is not required or available, is not consistent with the risk information described in the general investigational plan or elsewhere in the current application, as amended. For example, under this definition, hepatic necrosis would be unexpected (by virtue of greater severity) if the investigator brochure referred only to elevated hepatic enzymes or hepatitis. Similarly, cerebral thromboembolism and cerebral vasculitis would be unexpected (by virtue of greater specificity) if the investigator brochure listed only cerebral vascular accidents. "Unexpected," as used in this definition, also refers to adverse events or suspected adverse reactions that are mentioned in the investigator brochure as occurring with a class of drugs or as anticipated from the pharmacological properties of the drug, but are not specifically mentioned as occurring with the particular drug under investigation.
- **Attribution:** An assessment of the relationship between the adverse event and the protocol treatment, using the following categories.

ATTRIBUTION	DESCRIPTION
Unrelated	The AE is clearly NOT related to treatment
Unlikely	The AE is doubtfully related to treatment
Possible	The AE may be related to treatment
Probable	The AE is likely related to treatment
Definite	The AE is clearly related to treatment

- **CTCAE:** The NCI Common Terminology Criteria for Adverse Events provides a descriptive terminology that is to be utilized for AE reporting. A grade (severity) is provided for each AE term.
- **Expectedness:** Any adverse event, the type or severity of which is consistent with the current investigator's brochure, product label, and/or the protocol document.

Reporting Procedure

Internal Reporting Requirements: All events meeting the definition of a serious adverse event should be reported according to the internal departmental SAE checklist and SAE form. Copies should be sent to:

1. Investigator
2. [contact]
3. Local Institutional Review Board when reporting requirements are met.

SAEs, whether related or not related to study drug, and pregnancies must be reported to BMS within 24 hours \ 1 Business Day of becoming aware of the event. SAEs must be recorded on the internal departmental SAE form.

SAE Email Address: [contact]

SAE [contact]

If only limited information is initially available, follow-up reports are required. (Note: Follow-up SAE reports should include the same investigator term(s) initially reported.)

If an ongoing SAE changes in its intensity or relationship to study drug or if new information becomes available, a follow-up SAE report should be sent within 24 hours \ 1 Business Day to BMS using the same procedure used for transmitting the initial SAE report.

All SAEs should be followed to resolution or stabilization.

In addition to completing appropriate patient demographic and suspect medication information, the report should include as applicable the following information that is available at the time of report within the Sections of the departmental SAE form:

- CTCAE term(s) and grade(s)
- current status of study drug
- all interventions to address the AE (testing and result, treatment and response)
- hospitalization and/or discharge dates
- event relationship to study drug

Follow-up Reports: Additional information may be added to a previously submitted report by adding to the original departmental SAE form and submitting it as follow-up or creating supplemental summary information and submitting it as follow-up with the original departmental SAE form.

Reporting adverse events to the responsible IRB: In accordance with applicable policies of the University of Pittsburgh Institutional Review Board (IRB), the Investigator will report, to the IRB, any observed or volunteered adverse event that is determined to be 1) *associated with the investigational drug or study treatment(s)*; 2) *serious*; and 3) *unexpected*. Adverse event reports will be submitted to the IRB in accordance with the respective IRB procedures.

Applicable adverse events will be reported to the IRB as soon as possible and, in no event, later than 10 calendar days following the sponsor-investigator's receipt of the respective information. Adverse events which are 1) associated with the investigational drug or study treatment(s); 2) fatal or life-threatening; and 3) unexpected will be reported to the IRB within 24 hours of the Sponsor-Investigator's receipt of the respective information.

Follow-up information to a reported adverse event will be submitted to the IRB as soon as the relevant information is available. If the results of the Investigator's follow-up investigation show that an adverse event that was initially determined to not require reporting to the IRB does, in fact, meet the requirements for reporting; the Investigator will report the adverse event to the IRB as soon as possible, but in no event later than 10 calendar days, after the determination was made.

5.4 Dose Modifications

All toxicity grades below are described using the NCI Common Terminology Criteria for Adverse Events (CTCAE) version 4.0.

All appropriate treatment areas should have access to a copy of the CTCAE version 4.0. A copy of the CTCAE version 4.0 can be downloaded from the CTEP website (<http://ctep.cancer.gov>).

The use of colony stimulating factors (G-CSF, GM-CSF), and amifostine are explicitly discouraged. Erythropoietin stimulating agents, such as erythropoietin, and darbepoetin, are prohibited.

5.5 Supportive care and Other Assessments

Patient Reported Outcomes (PROs)

Quality of Life (QOL) assessments will be performed at baseline, end of treatment, and at 3, 6, 12, and 24 months after completion of treatment. If an additional tumor assessment is done prior to 3 years from study entry, one final QOL assessment is requested. QOL will continue to be collected for all patients post recurrence.

Paper questionnaires will be completed by the patient, and then data from the questionnaire should be provided within 7 days of completion. The original copy needs to be kept in the study subject's research binder.

Rehabilitation

It is strongly encouraged that all patients be referred for an assessment by a certified physical therapist after the completion of concurrent therapy. Components of the evaluation should include: neck shoulder and jaw range of motion, general conditioning level, the degree of treatment related fatigue, and postural issues. Patients with significant levels of deconditioning, postural abnormalities, or decrease in range of motion may require physical therapy. Occupational therapy may be needed in patients with extreme degrees of dysfunction. Patients with lymphedema should be referred for lymphedema therapy which should include: education, manual lymph drainage and the use of compression garments.

Speech and Language Pathology

Swallowing assessment and therapy is considered a critical component of care for all head and neck cancer patients. An MBS study will be required at baseline and after treatment as standard-of-care for patients with swallowing dysfunction. Assessments should be done by a trained Speech-Language Pathologists (SLP). The SLP should be consulted during treatment planning and should provide routine follow-up throughout the trajectory of the patient's treatment and recovery. The treating physician should communicate with the SLP to coordinate care in those patients found to have significant swallowing abnormalities. Critical component of the swallowing evaluation should include: 1) identification of any swallowing abnormalities, 2) recommendations for further testing, 3) formation of a treatment plan, 4) dietary recommendations, and 5) clear identifications of patients at risk for aspiration. Patients should be referred immediately for evaluation if any of the following "trigger symptoms" are identified: coughing or clearing the throat before, during or after eating, inability to control food, liquids or saliva in the oral cavity, complaint of difficulty swallowing or food "sticking" in the throat, nasal regurgitation of food, or pocketing of food in the cheek.

All supportive measures consistent with optimal patient care will be given throughout the study.

5.6 Duration of Therapy

- Patients will receive protocol therapy unless:
- Treatment is interrupted for 4 consecutive weeks; patient's protocol treatment will be discontinued
- Extraordinary Medical Circumstances: If at any time the constraints of this protocol are detrimental to the patient's health, protocol treatment should be discontinued
- Patient develops unacceptable toxicity; then the patient will discontinue protocol therapy
- Patients may withdraw consent and withdraw from the study at any time for any reason

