Subjects may be dosed no less than 12 days between doses. A dose given more than 3 days after the intended dose date will be considered a delay. A maximum delay of 6 weeks between doses is allowed.

Treatment Compliance

Treatment compliance will be monitored by drug accountability as well as the subject's medical record and eCRF.

Destruction of Study Drug

For this study, study drugs (those supplied by BMS or sourced by the investigator) such as partially used study drug containers, vials and syringes must be destroyed on site.

Any unused study drugs can only be destroyed after being inspected and reconciled by the responsible Study Monitor unless study drug containers must be immediately destroyed as required for safety, or to meet local regulations (eg, cytotoxic agents or biologics).

On-site destruction is allowed provided the following minimal standards are met:

- On-site disposal practices must not expose humans to risks from the drug.
- On-site disposal practices and procedures are in agreement with applicable laws and regulations, including any special requirements for controlled or hazardous substances.
- Written procedures for on-site disposal are available and followed. The procedures must be filed with the site's standard operating procedures (SOPs) and a copy provided to BMS upon request.
- Records are maintained that allow for traceability of each container, including the date disposed of, quantity disposed, and identification of the person disposing the containers. The method of disposal, i.e., incinerator, licensed sanitary landfill, or licensed waste disposal vendor must be documented.
- Accountability and disposal records are complete, up-to-date, and available for the Monitor to review throughout the clinical trial period.

If conditions for destruction cannot be met the responsible Study Monitor will make arrangements for return of study drug.

It is the investigator's responsibility to arrange for disposal of all empty containers, provided that procedures for proper disposal have been established according to applicable federal, state, local, and institutional guidelines and procedures, and provided that appropriate records of disposal are kept.

9. Statistical Considerations

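### Section 5.6 ends protocol treatment after a 4-week interruption, while Sections 5.2 and 8 allow nivolumab delays of 6 weeks, and no choice of starting point makes the rules agree for 4-weekly adjuvant dosing

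*Combined protocol and SAP*

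**What the plan says.** **Stopping after an interruption.** Four statements bear on this.

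- Section 5.6 (Duration of Therapy): "Treatment is interrupted for 4 consecutive weeks; patient's protocol treatment will be discontinued". It states no exception and does not say when the 4 weeks begin.
- Section 5.2, dose-delay paragraph: "Treatment delay up to 6 weeks for nivolumab from the last dose are allowable". Beyond that, "any dose delays greater than these will require approval from the medical co-chair".
- Section 5.2, Criteria to Resume Nivolumab Dosing: "Dose delay of nivolumab which results in treatment interruption of > 6 weeks requires treatment discontinuation, with exceptions as noted above". No starting point is given.
- Section 8, Dosing window: "A maximum delay of 6 weeks between doses is allowed".

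**What counts as a late dose.** Section 8 says "A dose given more than 3 days after the intended dose date will be considered a delay" and names no phase. Section 5.2 schedules adjuvant doses "every 4 weeks (+/- 7 days" and concurrent doses every 2 weeks with a margin of 2 days. The note opening Section 7 gives a margin of 1 week for scheduling treatment in general.

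**The concern.** The limits differ, and one cannot simply say that they govern different things. Section 5.2 under Criteria to Resume uses the same notion as Section 5.6, an interruption of treatment that leads to discontinuation, but with more than 6 weeks in place of 4.

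The situation is foreseeable. Under Section 5.2, most non-skin drug-related adverse events of Grade 2 or higher lead to a nivolumab delay. Section 9.2 plans approximately 25 UPMC sites and up to 5 external sites. Two patients with the same course could be stopped at one site and continued at another, depending on the section followed. That bears on patient care and on exposure. In a single-arm trial it also makes it less clear which regimen the PFS result describes.

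**Working it through.** The plan gives no figure to reproduce. The check is calendar arithmetic, with every limit expressed in days since the last dose given.

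**Inputs**

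- Section 5.6 limit: 4 weeks = 28 days, starting point not stated.
- Sections 5.2 and 8 limit: 6 weeks = 42 days. The dose-delay paragraph of Section 5.2 counts from the last dose, Section 8 speaks of delay between doses, and the Criteria to Resume state no starting point.
- Dosing interval: 14 days during radiotherapy, 28 days in the adjuvant phase.

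**Formula.** A limit of L days falls on day L if the clock starts at the last dose. It falls on day (interval + L) if the clock starts at the missed due date.

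| Section 5.6 counted from | 6-week rule counted from | 2-weekly: 5.6 vs 6-week rule | 4-weekly: 5.6 vs 6-week rule |
|---|---|---|---|
| last dose | last dose | 28 vs 42 | 28 vs 42 |
| due date | due date | 14+28 = 42 vs 14+42 = 56 | 28+28 = 56 vs 28+42 = 70 |
| due date | last dose | 42 vs 42 | 56 vs 42 |
| last dose | due date | 28 vs 56 | 28 vs 70 |

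**Results**

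1. With a common starting point (rows 1 and 2) the gap is 14 days in either phase. In that band Section 5.6 discontinues and the 6-week rules allow resumption.
2. In row 3 the rules coincide at day 42 for 2-weekly dosing. For 4-weekly dosing they differ by 14 days in the other direction, and Section 5.6 becomes the looser rule.
3. Row 4 does not fit the dose-delay paragraph of Section 5.2, which counts from the last dose. It is shown only because the Criteria to Resume name no clock. It widens the gap.
4. No row gives agreement for 4-weekly dosing.
5. If Section 5.6 counts from the last dose, its trigger falls on day 28, which is the scheduled day of the next adjuvant dose.

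**Beyond 6 weeks.** The dose-delay paragraph of Section 5.2 leaves room for co-chair approval. The Criteria to Resume require discontinuation subject to exceptions that they do not list. Section 8 gives 6 weeks as a maximum with no exception.

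**Late doses.** A 4-weekly dose is due on day 28. The Section 5.2 window runs to day 28 + 7 = 35, and the Section 8 delay begins after day 28 + 3 = 31. A dose on days 32 to 35 is therefore in window and delayed at once. A 2-weekly dose is due on day 14. The Section 5.2 window ends on day 16 and the Section 8 delay begins after day 17, so those two do not overlap. The Section 7 margin runs to day 21 and overlaps the Section 8 delay on days 18 to 21.

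**The case against.** **The clocks may differ.** Section 5.2 counts from the last dose, and Section 5.6 could be meant to count from the missed due date. This stands for the concurrent phase, where both limits then fall on day 42. It does not rescue the adjuvant phase, where they fall on days 56 and 42.

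**Section 5.6 speaks of treatment, not of nivolumab.** During radiotherapy, a patient whose nivolumab is held is still being irradiated, so Section 5.6 may arguably not be engaged. In the adjuvant phase nivolumab is the only protocol treatment (6 of the 9 doses), so the rules must meet there. Radiotherapy breaks have their own limit of 5 treatment days in Section 5.1.

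**The exceptions may refer to the co-chair approval.** If so, the two parts of Section 5.2 agree beyond 6 weeks. That is plausible, but the text does not say it, and Section 5.6 carries no exception at all.

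**The 3-day definition may have been written for 2-weekly dosing.** The 12-day minimum interval in the same paragraph of Section 8 equals 14 − 2 days, which suggests this. Section 8 names no phase, however. In any case it attaches no consequence to a dose more than 3 days late and goes on to allow longer delays. The point is therefore about labelling and does not change whether a dose may be given.

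**Stronger readings that the documents do not support**

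- A reader might infer that any patient 5 weeks off nivolumab must stop under one section and may continue under another. That depends on the clock. Counted from the last dose, 5 weeks in the adjuvant phase is day 35, the last day of the normal window.
- A reader might infer that every interruption of 4 to 6 weeks is classified in opposite ways. That needs a common starting point, which the documents do not set.
- A reader might extend the late-dose overlap to all 6 adjuvant doses. The first has its own start range, the second or third week after radiotherapy, with no single intended day. The clear overlap concerns the 5 later doses.
- A reader might expect an effect on the count of protocol deviations. The documents define deviations for radiotherapy dose, volume and breaks. They nowhere make a late nivolumab dose a deviation.

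**Conclusion.** The contradiction over stopping is real. On a common clock it leaves a 14-day band of opposite instructions. For 4-weekly adjuvant dosing the rules conflict under every combination of starting points; for 2-weekly dosing only one combination reconciles them. This rests on the current wording and on nivolumab being the only protocol treatment after radiotherapy. It implies no view on which limit is right.

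The late-dose inconsistency is minor.

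The consequences lie in who continues nivolumab, how much they receive, and how clearly the tested regimen is defined. No sample-size, power or alpha figure depends on this point. Under Section 5.7, patients who stop early are still followed until progression, so stopping does not in itself remove them from PFS follow-up. The documents give no basis for estimating how many patients would fall in the disputed band.

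**What to change.** Reconcile Section 5.2 (the dose-delay paragraph, the adjuvant schedule and the Criteria to Resume), Section 5.6, the scheduling note in Section 7 and the Dosing window in Section 8, so that together they state:

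- one interruption limit for each dosing phase, with its starting point (last dose or missed due date);
- one rule for what happens beyond that limit, including whether co-chair approval is available and which exceptions are meant;
- one definition of a delayed dose for each phase, consistent with the dosing window of that phase, including how the first adjuvant dose is treated.

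The sponsor must set the values. The cost is protocol wording only, with no change to the sample size or the primary analysis.
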